In Valparaíso, an important part of the team of this project developed the "Eco Barrio Solidario" Program between the years 2015 – 2019, based on the principles of the community approach of the National Mental Health Plan in our country. The objective was to strengthen intersectoral links (Health, National Service for Minors, Education and Community Organizations) to promote environments that facilitate the well-being and MH of children in the Baron Territory, Placeres and Quebrada Verde. The results were as follows: Regarding the problematization and through a participatory process, it was concluded a dismantling of the intersectoral network that intervenes in the process of development of the mental health of the child and youth population of Valparaíso in general and of each territory corresponding to the CESFAM Baron, Quebrada Verde and Placers. Specifically, the representatives of the education sector alluded to the difficulty in referral and access, the representatives of the Primary Health Care (PHC) to the need for an ecological approach, SENAME to the presence of different languages and logics, lack of space for communication with health and the Child and Adolescent Unit of the Psychiatric Hospital of El Salvador to the need for comprehensive treatments and support in early screening. Regarding referrals, through the ECO form, significantly higher figures are reported to PHC than to specialized care service, in this case Child and Adolescent Outpatient Unit, Salvador Hospital considering the years 2016, 2017 and 2018. In turn, in 2020, the Joint Health-Education Commission (COMSE) of Valparaíso reinforces the need for a rearticulation of intersectionality to face the socio-health crisis in educational communities, collecting expectations of constant and contextualized training to the territory, greater resolutivity and community participation,

collecting elements of the aforementioned ECO Barrio Solidario program for children, which had good valuation from its participants.

Therefore, at the end of the COVID-19 pandemic we will face an increase in mental health problems in children, for which it is essential to improve the ability to identify them through their teachers and parents, as well as the articulation of a community network and local services to meet these needs, Both aspects being the components of the intervention that seeks to develop and evaluate in this proposal.

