Parallel to the construction of the CMH Literacy program for teachers, the "ECO BARRIO SOLIDARIO" strategy will be implemented in one of the neighborhood with modifications according to the new health and contextual scenario, which will be called "ECO-Barrio Network". The strategy of the ECO-Barrio Network is feasible to replicate given that in Primary Health Care (PHC) there are the Joint Commissions of Health-Education (COMSE), which aim to link CESFAM with the Educational Establishments that converge in a territory, to develop strategies for prevention, participation and health promotion in educational communities. Particularly in Valparaíso, since 2020 and in the face of the socio-health crisis due to COVID-19, it is developing a COMSE 2.0 strategy, whose objectives are: 1) to re-activate the COMSE meetings with the participation of Mental Health Managers of each school, psychosocial duo of the PHC health team and in charge of participation and promotion of CESFAM. 2) Develop a socio-educational process for COMSE participants to improve the referral and follow-up of cases from the educational community to PHC, in addition to the development of prevention and promotion strategies in MH and 3) Develop a containment, prevention and promotion device in MH for the educational communities of the educational establishments of the polygon associated with each CESFAM. These new objectives of COMSE 2.0 are aligned with the ECO-Barrio Network strategy and with this project. The contribution of the ECO-Barrio Network strategy will be to systematically convene potential participants of the COMSE, including all relevant participants in the CMH of that neighborhood (Health from primary care with the CESFAM and CECOF that correspond plus specialized care with the Outpatient Unit of Child and Adolescent Psychiatry of the Psychiatric Hospital of Salvador (HDS), SENAME in its different programs and others such as Life Skills (HPV). In addition, from the articulation with the Secondary level of Mental Health and the link with the chair of Child Psychiatry of the University of Valparaíso, the ECO-neighborhood Network will be able to organize and provide training, generate the case monitoring system on an online platform and evaluate the implementation process in the two selected neighborhoods which will serve as an input for a potential replication to other territories of Valparaíso.

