## **2.3. RESEARCH HYPOTHESES OR ASSUMPTIONS**

1. Teachers who participate in a Child Mental Health Literacy program are able to significantly improve their knowledge regarding the identification of these problems and the delivery of first aids.
2. The establishments that participate in this training program significantly improve the detection rate of children with mental health problems.
3. The relevance of the diagnosis made by teachers when referring children with mental health problems to the corresponding CESFAM is greater than 80%.
4. The health-education networks where an intervention is carried out to articulate the referral of girls and girls with mental health problems, reduce the waiting time that goes between the referral and the first health care.

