### **3. METHODOLOGY, ETHICS AND PLANNING**

#### **3.1. METHODOLOGY AND PROCEDURES**

Research design. This project corresponds to an evaluation of the preliminary effectiveness and feasibility of a multi-component pilot intervention. The program will be evaluated through a cluster randomized controlled trial (RCT)

The project activities are organized around two clearly defined stages: one of participatory construction, and another of evaluation of the effectiveness and feasibility of the pilot intervention. They are explained in detail below.

Effectiveness is studied through a mixed design (subtype DEXPLIS, explanatory design sequence), which begins with a quantitative study of quasi-experimental type (comparing equivalent intervention and control facilities) and is followed by a qualitative study to analyze the implementation process and results of the pilot to intervention(including its barriers and facilitators).

The reliability is studied through indicators of participation of teachers in the intervention (initial interest and retention over time), by the satisfaction of teachers and those who participate in the articulation of local health-education networks, and with the analysis of barriers and facilitators at all levels.

Universe and sample. The universe to which the results of this study could be extended are public educational establishments. For this study, two neighborhoods of the commune of Valparaíso were selected. Therefore, the selection of the territories is not random, but the selection of the 2 establishments in each territory is. The inclusion criteria are that they are public schools and have 1st to 8th levels of primary education. The list of establishments that exist in that sector and that meet the inclusion criteria will be taken and will be selected using some random method, 2 schools of each neighborhood (4 in total) will be initially assigned to the intervention and 2 will serve as a control (four in total). As previously described, in a second moment the intervention will be carried out in the establishments that served as control for ethical reasons.

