1. The first stage (months 1 to 18) The component of the intervention aimed at articulating educational establishments with mental health devices (CESFAM teams and secondary level in Health), within specific territories, whose purpose is to expedite the care of these children, will be implemented. It is the so-called ECO-Barrio Network, for whose implementation a working committee will be formed for each sector where the study is implemented, with representatives of all these institutions, in addition to the I. Municipality of Valparaíso. This committee will begin by analyzing the barriers that hinder the referral of children with mental health problems, and then establish a specific work plan in each sector (with objectives, activities, goals and deadlines). The activities of this plan will be implemented in parallel to the intervention with the teachers, in the second part (months 7 to 18, so that the times are concordant). In addition, follow-up meetings of referrals will be held with 1 representative of each CESFAM with ECO BARRIO coordinator and the 4 schools intervened, in a modality that includes virtuous meetings with bimonthly frequency. Finally, this stage of work will include at least one weekly meeting of the FONIS team with advisors and coordinators of RED ECO and Literacy Program.
2. The second stage (months 1 to 12) consists of the participatory construction of the contents of a training program on children's mental health, aimed at teachers of public educational establishments, which will use e-learning (with asynchronous and synchronous activities) and whose contents will be based on their experience with respect to of the problems they distinguish, the way they identify them, the obstacles they have in handling them, and the opportunities for support they can provide (including the relationship with their parents). To collect the experience of the teachers, a working group will be created in each establishment participating in the project, which will collect the experience of the teachers on this subject. In addition, in-depth individual interviews will be conducted. Then, one or two teachers from each group (from each establishment) will be invited to participate in a team with psychologists and psychiatrists from the project, to design the course together. The contents and methods of the course will be made by the research team, under the supervision of the team that includes teachers, technical advisors and audiovisual equipment.

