3. The third part (months 12 to 24) consists of carrying out a pilot test taking 4 educational establishments located in two different territories of the commune of Valparaíso, in which the intervention will be carried out, and its results will be compared with 4 other equivalent educational establishments, from those same territories, which serve as control. Pre- and post-intervention assessments will be carried out, using a children's mental health knowledge survey, while referrals from facilities to the corresponding CESFAM will be recorded. Results will be compared between intervention and control results. Information is also collected to assess the participation of teachers in the intervention (feasibility analysis).

At the end of the intervention in the establishments that were the object of it, the quantitative indicators and results that were collected will be synthesized, and a qualitative analysis will be carried out (DEXPLIS design), based on discussion groups that involve the interested parties (teachers, mental health professionals and managers of both sectors). in which the results and achievements will be analyzed, barriers and facilitators of the process will be established, all of which will allow to complete the evaluation in a participatory way and to improve the components of the intervention, based on the empirical experience carried out.

After the end of the intervention, the intervention will also be carried out in its two components (teachers and health-education network) in the 4 establishments that served as control. In this way, an ethical requirement of not depriving the rest of the participants of a beneficial intervention is met. (Months 18 to 24)

Indicators, instruments and analysis procedures. For the detailed description of this point, the effectiveness analysis and the feasibility analysis of the pilot intervention are separated.

1) Evaluation of the effectiveness of the intervention. The effectiveness evaluation is based on comparing the following indicators between intervention and control establishments.

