- a) Level of knowledge of the teachers, using an *ad hoc* questionnaire, which is built in the phase prior to the intervention and validated by this team (which incorporates teachers). The conceptual framework of literacy in child and adolescent mental health will be used. This questionnaire will include all the aspects that are part of the training program aimed at teachers and will allow them to obtain scores for their different modules or dimensions. A test and semantic adaptation will be carried out with teachers from establishments in other sectors of the commune, which do not participate in the project, prior to its use within the project. It is expected that in the initial assessment (baseline), the results will be similar in the teachers of the intervention and control establishments. At the end of the intervention it is expected that scores have improved significantly in intervention facilities and have not changed in control facilities.
- b) Rates of referral of mental health problems in children. In each project establishment (intervention and control) a centralized register will be kept of the children indicated by their teachers who require mental health care during the intervention. This will also allow for centralized coordination for referral to the relevant CESFAM. In this way the detection rate can be calculated.
- c) Waiting time between referral from the educational establishment to professional care at the corresponding CESFAM. This indicator is obtained from the centralized register in each educational establishment, which includes the date on which it coordinated with CESFAM for its attention, and the registration of the first attention in the latter. The time elapsed between the two is the waiting time that will be used as an indicator.
- d) Rate of accuracy for referral of children with suspected psychiatric disorders from the school to health care. Each “case” referral will apply the Strength and Difficulties Questionnaire (SDQ). 25 items (scale 0-2).

2) Evaluation of the feasibility of the intervention. Feasibility assessment uses a combination of quantitative (indicator) and qualitative methods, which are described below.

- a) Level of interest of teachers in the intervention: It is estimated through the percentage of teachers who agree to start the training course, out of the total number of teachers who were invited (which would be the totality of each educational establishment).

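### With intervention and control schools in the same territories, the waiting-time comparison cannot isolate or fully capture the network's effect (objective 6, hypothesis 4)

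*Combined protocol and SAP*

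**What the plan says.** Hypothesis 4 (section 2.3) is about networks: those with an articulation intervention "reduce the waiting time that goes between the referral and the first health care". Objective 6 (section 2.4.2) asks the same of the ECO-Barrio Network. The indicator in section 3.1 is "Waiting time between referral from the educational establishment to professional care at the corresponding CESFAM", counted from the date the school coordinated with the CESFAM to the first attention there.

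Section 3.1 evaluates effectiveness by comparing indicators between intervention and control schools. The allocation is described as "2 schools of each neighborhood (4 in total) will be initially assigned to the intervention and 2 will serve as a control", and the pilot stage takes as comparators "4 other equivalent educational establishments, from those same territories, which serve as control".

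The network is set up at a higher level than the school. In section 3.1 "a working committee will be formed for each sector where the study is implemented, with representatives of all these institutions", and that committee writes a work plan for its sector. Section 2.1 builds the network on the health-education commissions that tie a CESFAM to the schools of its territory, and has it convene people "including all relevant participants in the CMH of that neighborhood". Both arms keep a centralized register of referred children: "This will also allow for centralized coordination for referral to the relevant CESFAM".

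Two statements point the other way. Referral follow-up meetings are described for the four intervened schools only. Control schools are to receive both components, network included, after the comparison (months 18 to 24).

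**The concern.** The network works largely on the territory and its clinic, whereas the comparison is between schools inside the territory. If the sector committee gets the CESFAM to see children sooner, children from control schools should benefit too, and that gain is invisible between arms. Any difference that does appear comes from a package: intervention schools receive the literacy course and the school-specific network elements together.

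Objective 6 could therefore be answered wrongly. A useful network could give a null result. A difference could reflect the literacy program, or intervention children being seen ahead of control children, with no overall reduction. The pilot is meant to inform a larger study, so either error would carry forward.

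**Working it through.** **What the contrast contains.** Let B be the usual wait and T the reduction from network changes that reach every school of a territory. Let S be the reduction from network elements confined to intervention schools, L any change in intervention-school waits due to the literacy program (for example through case mix), and Q any change from a heavier load at a common CESFAM.

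- Intervention wait = B − T − S + L + Q
- Control wait = B − T + Q
- Difference = −S + L

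Objective 6 concerns T + S. T and Q cancel, and S cannot be separated from L. The documents do not give the split between T and S.

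**The plan's own figure.** No mean, SD, target reduction, intraclass correlation (ICC) or sample size is given for waiting time. The only sample size, 56 children per group, is for the detection rate (0.3 versus 0.6, 90% power). It reproduces with the pooled two-proportion formula: two-sided (1.960 × √0.495 + 1.282 × √0.45)² / 0.09 = 55.7, so 56. The one-sided test that the text describes gives 46. The figure says nothing about waiting time.

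**Referral volume.** Inputs from section 3.1: 240 pupils per school, and 9 identified cases per 100 per year rising to 18. I assume that identified cases become referrals and that schools split evenly over two neighborhoods.

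- Using 480 pupils per arm in total, each neighborhood has 240 per arm. Usual: 480 × 0.09 = 43.2. With doubling: 240 × 0.09 + 240 × 0.18 = 64.8. Extra: 21.6.
- Using four schools per arm, each neighborhood has 480 per arm. Usual: 960 × 0.09 = 86.4. With doubling: 43.2 + 86.4 = 129.6. Extra: 43.2.

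Both are a 50% rise in study-school referrals. The proportional rise at the CESFAM would be smaller, since other referrals arrive there too.

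**Dilution.** Let c = T/(T + S), the share of the network effect that also reaches control schools, and take L = 0. The expected contrast is (1 − c) times the network effect, and the sample size needed for fixed power grows by 1/(1 − c)²: 1.78 at c = 0.25, 4 at 0.5 and 16 at 0.75.

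Power, one-sided 5%, for an assumed network effect of d SD:

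Φ[(1 − c)d / √(1/n_control + 1/n_intervention) − 1.645]

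Yearly referrals are 480 × 0.09 ≈ 43 and 480 × 0.18 ≈ 86, or 86 and 173 with 960 pupils per arm. For d = 0.5, c = 0.5 and 43 versus 86: √(1/43 + 1/86) = 0.187, 0.25/0.187 = 1.34, and Φ(1.34 − 1.645) = 0.38.

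| c | d = 0.5, 43 vs 86 | d = 0.5, 86 vs 173 | d = 0.3, 43 vs 86 |
|---|---|---|---|
| 0 | 0.849 | 0.984 | 0.485 |
| 0.25 | 0.642 | 0.884 | 0.330 |
| 0.5 | 0.380 | 0.599 | 0.200 |
| 0.75 | 0.165 | 0.243 | 0.107 |
| 1 | 0.050 | 0.050 | 0.050 |

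With an assumed ICC of 0.05 and 129/4 ≈ 32 referrals per school, the design effect is 1 + 31.25 × 0.05 = 2.56. The first column then starts at 0.511 and is 0.209 at c = 0.5. The values of d, c and the ICC are assumptions, not figures from the plan.

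**The case against.** The plan does intend a difference in network exposure. Follow-up meetings are for the intervened schools, and control schools are promised the network only in months 18 to 24. A reader might infer that the network serves both arms equally and that the contrast is empty; the documents do not support that. They do not say, however, how a sector committee's plan or a change in clinic intake would be withheld from control schools until month 18.

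A reader might also take one shared waiting list as fact. It is a strong inference from the territory structure and from the reference to each school's corresponding CESFAM. But the trial's CESFAMs are not named, and the sentence about "each territory corresponding to the CESFAM Baron, Quebrada Verde and Placers" (section 1.2) concerns the 2015–2019 program. Nothing describes how a list is ordered, so displacement of control children is a possibility only.

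Nor can one say that no pre-network wait will be collected. The register is described as running during the intervention, but the work-plan rows for objective 6 are not in the text available for review. Section 3.1 places the sector plan's activities in months 7 to 18, after the set-up months.

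Finally, other passages describe different layouts. Section 2.1 and the opening of the fieldwork description put the network in one neighborhood, while section 2.4.2 and section 4.1.2 say two. The work plan (section 3.3) draws two comparison schools from a neighborhood without the intervention. On that last layout the shared-clinic problem largely disappears, but network exposure becomes confounded with a neighborhood that was not chosen at random.

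This is also a pilot sized on objective 4, with objective 6 one of seven, which bears on severity.

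**Conclusion.** The concern holds in a limited form. With both arms in the same territories, the between-arm waiting-time comparison cannot isolate or fully capture the network's effect. It omits whatever reaches all schools of a territory and mixes the rest with the literacy program. It is diluted and confounded, not uninformative.

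The extent of dilution is unknown. On the assumptions shown, power is 0.849 with no spillover, 0.380 with half and 0.050 with complete spillover. Doubled detection would raise study-school referrals by 50%. This could lengthen waits in both arms if they share a CESFAM, which is inferred rather than stated. The sponsor should fix this, but it does not undermine the trial as a whole.

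**What to change.** 1. Reconcile sections 2.1, 2.4.2, 3.1, 3.3 and 4.1.2 on the number of network neighborhoods and on where control schools lie.
2. State which network elements control schools receive before month 18, and name the CESFAM of each school.
3. Keep the randomized comparison, but state that it estimates only the school-level added effect of the combined intervention. A null result does not show that the network failed, and a shorter intervention wait alongside a longer control wait is not an overall reduction.
4. For objective 6, add a descriptive comparison of absolute waits and referral volumes, by arm and CESFAM, with the same schools' referrals before the network's activities begin. Use existing CESFAM records where available, and the same start-date definition in both arms.

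The cost is protocol wording and a small data extraction; the documents do not show how complete the earlier records are. The before-after comparison is open to time trends and to the extra referrals produced by the literacy program, so it must be labeled descriptive.

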### **2.4.2. SPECIFIC OBJECTIVES**

1. Build in a participatory way the contents of a literacy program in Child Mental Health (CMH) with teachers of Public Educational Establishments (PS) and key actors, from the commune of Valparaíso.
2. Implement the strategy of articulation in a network of CMH (ECO-Neighborhood Network) between schools, Primary and Secondary Health Care, Municipality, collaborating agencies of SENAME and other relevant programs in 2 territories of the commune of Valparaíso.
3. To evaluate whether the Child Mental Health Literacy program, aimed at teachers in public educational establishments, manages to significantly improve their knowledge in this regard.
4. To assess whether teachers participating in the CMH Literacy program significantly improve the detection rate of these problems among their pupils.
5. To evaluate whether the relevance of the research for referral from educational establishments to the corresponding CESFAM is greater than 80%.
6. To evaluate whether the health-education articulation strategy (ECO-Barrio Network) significantly improves waiting times between referral and the first care received by a child with a possible mental health problem.
7. Evaluate indicators of feasibility of the multicomponent intervention, which are useful for a future escalation (interest of teachers to participate, retention in the intervention, degree of satisfaction of all participants, facilitators and perceived barriers).

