To calculate the necessary sample size, the following parameters were considered: a prevalence of mental disorders of 27.8% and an identification rate of 30% of these cases (9 cases per 100 children, per year). This indicator (which corresponds to scenario 2 and specific objective 4) was taken as one of the most important achievements and reflects the impact of the intervention as a whole. To accept the fulfillment of our hypothesis, it will be necessary to double the identification rate to 60% of cases (18 cases per 100 children, per year). In this way, it is a comparison of proportions, where:  $p_1 = 0.3$ ,  $p_2 = 0.6$ , a confidence level of 95% for a unilateral test and a power level of 90%, 56 children are needed in each group. However, it is expected to work with a much larger sample: if it is considered that in each establishment there are 30 children per grade and only one course per level (from 1st to 8th grade). This would lead us to a potential sample of 240 children per establishment, which implies 480 in intervention facilities and 480 in control facilities.

Development of fieldwork. The development of the fieldwork has three fundamental stages: 1) Implementation of the ECO-Neighborhood Network strategy in the 1 selected neighborhood, (months 1

to 18), 2) the participatory construction of the components of the intervention (months 12 months); and 3) pilot-level evaluation of this intervention (months 12-24).

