### 3.3. WORK PLAN

Specific Objective	Activity	Months																							
		1	2	3	4	5	6	7	8	9	10	11	12	13	14	15	16	17	18	19	20	21	22	23	24
1-Build in a participatory way the contents of a Literacy program in CMH	1-Presentation of the Ethics Committee Project	x																							
	2- Random selection of the 4 PS		x																						
	3-Contact and invitation to working meetings of key informants of the territories and PS		x	x																					
	4- Establish work teams in each selected PS			x																					
	6- Participatory design of the literacy program			x	x	x	x																		
2. Implement the ECO-Barrio network strategy	1- Contact with key agents of the CMH network	x																							
	2-Form a committee in each sector with the representatives of the institutions of the intersectoral ecosystem in CMH	x																							
	3- Develop a participatory work plan with objectives, goals, activities, deadlines and managers.		x	x	x																				
	4-Bimonthly work and follow-up meetings.			x	x	x	x	x	x	x	x	x	x	x	x	x	x	x	x						
3. Assess whether the literacy program significantly improves knowledge in CMH	1- Recruitment of teachers to participate in the literacy intervention.			x	x	x	x																		
	2- Development of knowledge instrument in CMH			x																					
	3-Test of application of the instrument in PS of non-intervened sectors.				x																				
	4-Semantic adaptation of the instrument.					x																			
	5-Implementation of online literacy course (G1 and G2)							x	x	x	x	x	x	x	x	x	x	x	x						
	6 Evaluation of teachers intervened with instrument (pre and post intervention)							x					x							x					
4- Evaluate if the detection rate of CMH problems is significantly improved	1-Random selection of 2 PS similar to those selected in a neighborhood where the intervention has not been implemented				x																				
	2- Determine the detection rate in schools that received the literacy program compared to control schools												x										x		
5.Evaluate whether the relevance of referral to	1- Determine how many of the referred children enter Mental Health treatment (regardless of the device or level of complexity)						x	x	x	x	x	x	x	x	x	x	x	x	x						

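### Waiting time and referral accuracy are compared between arms only among referred children, a group the training is meant to enlarge and may change in mix, so these arm differences may not be like-for-like.

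*Combined protocol and SAP*

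**What the plan says.** Section 3.1, under the evaluation of effectiveness, states: "The effectiveness evaluation is based on comparing the following indicators between intervention and control establishments". Two of the four indicators can be observed only in referred children.

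- **1c, waiting time.** It runs from the date the school coordinates with the CESFAM to the first attention there: "The time elapsed between the two is the waiting time that will be used as an indicator". Objective 6 (section 2.4.2) asks whether the network strategy "significantly improves waiting times between referral and the first care received by a child with a possible mental health problem".
- **1d, accuracy.** This is the "Rate of accuracy for referral of children with suspected psychiatric disorders from the school to health care", with the SDQ applied to each referred case. No SDQ is planned for other pupils and no cut-off is given. The work plan (section 3.3) has a second version of referral relevance: "Determine how many of the referred children enter Mental Health treatment". Its denominator is again the referred children. Hypothesis 3 (section 2.3) concerns whether the relevance of the diagnosis when "referring children with mental health problems to the corresponding CESFAM is greater than 80"%, which is a threshold and not an arm difference.

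The sample-size paragraph in section 3.1 assumes "a prevalence of mental disorders of 27.8"%, with 30% of cases identified now and 60% needed for success. Nothing in the plan provides for severity adjustment, for stratification, or for a whole-enrolment denominator for 1c or 1d.

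**The concern.** Assignment balances the schools and their enrolled pupils. It does not balance the pupils whom teachers later refer, because the training is designed to alter that decision. A larger referred group is an explicit aim. A different mix is plausible: section 1.2 says schools cannot always tell which problems suit primary care and which need specialists, and training on that point could change who is referred.

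Section 3.1 delivers both the teacher training and the network to the intervention schools, and to the control schools only afterwards. A training-driven change in who is referred would therefore sit inside the same waiting-time contrast that objective 6 credits to the network. It could be misread as a network success or failure. The summary says the results will inform the design of a larger study, so a misreading would carry forward.

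**Working it through.** **Inputs from the plan (section 3.1, sample size):** prevalence 27.8%; identification 30% (control) and 60% (intervention); 480 children per arm. Four schools of 240 would give 960, so both are shown.

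**Inputs not in the plan (assumed, as ranges):** the severe share of cases, detection by severity, waits by severity, and the false-referral rate among non-cases.

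**1. The plan's own figures.** Identified cases per 100 children are 27.8 × 0.30 = 8.3 and 27.8 × 0.60 = 16.7; the plan prints 9 and 18. Per arm:

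- 480 children: 0.278 × 0.30 × 480 = 40 against 0.278 × 0.60 × 480 = 80.
- 960 children: 80 against 160.

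Either way the number of identified cases is planned to double in one arm. The plan's 56 children per group concerns identification and is not used here.

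**2. Waiting time with no service difference.** Let s be the severe share of all cases, d the detection of severe cases and D overall detection (0.30 or 0.60). The severe share among referred cases is f = s × d / D. The mean wait is f × 30 + (1 − f) × W, with W = 60 or 90 days for milder cases. Control d is 0.50 throughout the table.

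| s | trained d | f control | f trained | means, W = 60 (days) | means, W = 90 (days) |
|---|---|---|---|---|---|
| 0.3 | 0.7 | 0.500 | 0.350 | 45.0 vs 49.5 (+4.5) | 60.0 vs 69.0 (+9.0) |
| 0.3 | 0.8 | 0.500 | 0.400 | 45.0 vs 48.0 (+3.0) | 60.0 vs 66.0 (+6.0) |
| 0.5 | 0.7 | 0.833 | 0.583 | 35.0 vs 42.5 (+7.5) | 40.0 vs 55.0 (+15.0) |
| 0.5 | 0.8 | 0.833 | 0.667 | 35.0 vs 40.0 (+5.0) | 40.0 vs 50.0 (+10.0) |

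If detection doubles evenly (d = 0.30 and 0.60), then f = s in both arms and the difference is zero; for s = 0.5 and W = 90, both means are 60.0. If training raised the severe share among referrals, the sign would reverse.

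**3. Accuracy with an unchanged false-referral rate.** The share of referrals that are true cases is 0.278 × D / (0.278 × D + 0.722 × r), where r is the false-referral rate among non-cases.

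- r = 2%: 0.0834 / 0.0978 = 85.2%; 0.1668 / 0.1812 = 92.0%.
- r = 3%: 0.0834 / 0.1051 = 79.4%; 0.1668 / 0.1885 = 88.5%.
- r = 5%: 0.0834 / 0.1195 = 69.8%; 0.1668 / 0.2029 = 82.2%.

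At 3% and 5% the share crosses 80% through detection volume alone. These are true-case shares, not SDQ results. If the added cases are milder and less often SDQ-positive, 1d is pushed the other way.

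**4. Check on a tempting remedy.** Take s = 0.5, d = 0.5 against 0.7, waits of 30 and 90 days in both arms, and count children seen within 60 days per 100 enrolled. Only severe cases qualify: 27.8 × 0.5 × 0.5 = 6.95 against 27.8 × 0.5 × 0.7 = 9.73. The ratio is 9.73 / 6.95 = 1.40 with no change in service. That measure mixes detection with access.

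**The case against.** Five points can be made for the plan.

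- **Accuracy is a proportion of referrals by definition.** Hypothesis 3 and objective 5 set it against 80%. Whom teachers refer is what the training targets, so a changed mix is partly the effect itself. This stands for the threshold question. It does not cover the arm comparison, for which section 3.1 also lists 1d.
- **The severity shift is assumed.** No section says that missed cases are milder or that milder cases wait longer. Section 1.2 could point the other way: training might remove milder referrals. That section also reports requests for help as mainly school-disruptive (50%) and less often emotional (17%), so missed children may be quieter, not milder. This stands, and is why no direction can be given.
- **Adjusting for the SDQ would not restore comparability.** It is taken after assignment, only on referred children, and the informant is not stated. This stands, so SDQ-banded results can only be descriptive.
- **Detection is already expressed per 100 children.** True, but that covers neither waiting time nor accuracy.
- **This is a pilot sized on identification.** True, and it limits the weight of the point.

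A reader might infer that a programme which succeeds on detection must look worse on waiting time and accuracy. The documents do not support that: the waiting-time artefact may be zero or reversed, and accuracy may rise. Nor does hypothesis 2 predict a doubling of referrals. It speaks only of a significant improvement in detection. The doubling is in the sample-size paragraph and concerns true cases identified; total referrals include non-cases and need not double.

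**Conclusion.** The concern holds in a limited form. Indicators 1c and 1d are compared between arms within a group formed after assignment, one the training is planned to enlarge (about 40 against 80 identified cases at 480 children per arm) and may change in mix. The comparisons may therefore not be like-for-like, and the plan has no analysis that would show whether they are.

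Under the assumptions shown, the waiting-time artefact ranges from zero to about 15 days against the intervention. The true-case share of referrals could rise by about 7 to 12 percentage points (92.0 − 85.2 = 6.8; 82.2 − 69.8 = 12.4) with no change in false referrals among non-cases, while milder added cases would pull SDQ positivity down. Only the prevalence and the two identification rates come from the plan; the other inputs are illustrative. It would go too far to call either comparison biased in a known direction. The point is clearest for waiting time, because objective 6 credits that difference to the network.

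**What to change.** 1. **Accuracy (1d).** For the arm comparison, report SDQ-positive and SDQ-negative referrals per 100 enrolled children, by school and arm, with the SDQ cut-off fixed in advance. Assignment protects this denominator, and the two rates separate added detection from over-referral. Keep the proportion of referrals for the 80% threshold.
2. **Waiting time (1c).** Report it by SDQ band as well as overall. Label the banded results descriptive, because the SDQ is taken after assignment and only on referred children. State that a crude arm difference will not be attributed to the network alone.
3. **Optional whole-enrolment measure.** If children with a first attention within a fixed time per 100 enrolled is reported, label it a combined detection-and-access measure and not a test of hypothesis 4.

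The cost is small. The SDQ is already planned for each referral, the register already holds both dates, and enrolment counts are already needed for the detection rate. The downsides are a few more figures to report and sparse strata with four schools per arm.
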